- Electronic records (computer files, electronic databases, etc.) - CADRE project data will be stored on the CADRE server, which is maintained, backed-up, and secured in a locked server room by the Iowa City VA's Information Resources Management (IRM) department, and on VINCI. The server can only be accessed by individual with an IRM-created network account. Data are further secured using network directory permissions assigned by IRM at the direction of the Principal Investigator (PI). This ensures that only study personnel with the approval of the PI (in accordance with IRB requirements) have access to identifiable human subject/patient data. Additionally, files on the network that contain identifiable human subject data are password protected, and individual accessing the server on a client machine are instructed to password protect their screen saver in order to maintain data security. A random, unique identifier will be used to identify patients in electronic study datasets used for analyses. All direct identifiers will be removed from the study datasets before conducting analyses. The linkage between the unique identifier and identifying information resides on a secure VA server and is only available to IRB approved study personnel. Bank information will be collected only for the purpose of compensating subjects. It can be collected in one of 2 ways, whichever the subject prefers. The subject can be mailed a form to fill out and return via pre-paid postal envelope, or via secure fax. This information will be entered into our database which has all of the security measures described above. Any incidents involving loss of data, etc., will be reported immediately to the PI and data manager. Access to data will be terminated when a staff member is no longer on the research team. A HIPAA de-identified dataset will be shared with outside collaborators, all of whom are either covered to carry out the research by their local institutions, or whose local institutions have deemed the work with de-identified data does not constitute human subjects research. All HIPAA 18 identifiers will be removed, and a Data Manager, Statistician and Privacy Officer will review the data to ensure that all identifiable elements have been removed.

- [REDACTED]
- [REDACTED]
- [REDACTED]

X.5 Do the confidentiality protections indicated above allow only members of the research team to access the data/specimens?

No

X.6 Describe

A HIPAA de-identified dataset will be shared with outside collaborators, all of whom are either covered to carry out the research by their local institutions, or whose local institutions have deemed the work with de-identified data does not constitute human subjects research. All HIPAA 18 identifiers will be removed, and a Data Manager, Statistician and Privacy Officer will review the data to ensure that all identifiable elements have been removed.

X.7 Does your study meet the NIH criteria for a *Certificate of Confidentiality* or will you be applying for *Certificate of Confidentiality*?

No

XI. Data Analysis**XI.1 Describe the analysis methods you will use, including, if applicable, the variables you will analyze**

Qualitative Analysis (Aims 1 and 3): CFIR will guide the key domains/constructs queried in Phases 1 and 3 with key informants and in Phase 3 with RCT participants and providers (see below). The initial analytic approach to the interview data will use the constant comparison method, whereby we use open coding to identify salient issues and concerns raised by the participants across all of the groups. These open codes will be examined by the investigators in order to develop themes that pertain to the majority of participants, with a focus on addressing the specific aims of the study (rather than all emergent themes). These themes will also be analyzed for their potential "fit" with the CFIR model, i.e., their relevance to the concepts of intervention, outer and inner setting, individual characteristics, and implementation process. Assuming that there will be some degree of fit between emergent themes and conceptual domains, each conceptual domain will be summarized with reference to its applicability to refinements to the intervention as well as overall implementation processes. MAXQDA v12, a qualitative data analysis software program, will be used to assist this process. The codebook will be developed initially by [name] and [name] with subsequent co-investigator and qualitative team independent coding of transcripts. In Phase 3 this will be specific to RCT participation (WEB-ED+ versus WEB-ED).

Aim 2 Analyses: We will begin with bivariate analyses (i.e., chi-square test for proportions) to test significance of differences in care engagement between RCT arms. Care engagement is the primary outcome and will be operationalized by VA MH services receipt (yes/no). Our primary analyses will use logistic regression models to estimate the adjusted ORs for treatment engagement controlling for participant characteristics. The logistics regression models will provide an estimate of the association between health care engagement by RCT arm, controlling for covariates such as Veteran gender, prior VA enrollment, severity [screening scores] and complexity [multiple positive screens], patient-activation scores, and rurality. Potential confounding variables that will be assessed in all hypotheses include socio-economic variables (e.g., age, income, marital status), and military characteristics (e.g., months home

from deployment, rank). In addition, depending on the resulting proportions of Veterans who get care in various VA clinics (i.e., PC, PCMH, MH), we plan to conduct a multinomial logistic regression, treating RCT-arm as a covariate. We have used multinomial logistic regression previously to examine associations with three levels of VA health care use (all, some, none).

XI.2

Provide the rationale or power analysis to support the number of subjects proposed to complete this study.

We will aim for 2000 Veterans completing WEB-ED, with approximately 1100 completing the RCT. Not all 2000 will be eligible for the RCT. Based on our five prior studies, ~77-85% of WEB-ED participants screened positive on at least one of the MH screens (~70% screened positive on depression, PTSD, or substance use). We will assume that 70% will eligible for the RCT (~1400) and use adaptive randomization to assign positive-screener to each RCT arm; two-thirds to WEB-ED+ (~950) and one-third to Current WEB-ED (~450). There are no additional RCT participation activities for those in the Current WEB-ED arm, therefore attrition would be minimal. However, we anticipate there may be attrition among those assigned to WEB-ED+. Our CREATE multi-phase study resulted in attrition of ~30%. Therefore, we expect 650 completers for WEB-ED+. We have increased this sample size to have sufficient power to detect differences per RCT arm. This study is powered to detect whether WEB-ED+ increases VA MH care engagement compared to Current WEB-ED. In our prior work, half indicate that as a direct result of WEB-ED, they will follow up with a provider and 38% with a VA provider, although actual follow-up may be lower (our CREATE study is currently validating participant self-report with chart review data). This proposed study will document VA utilization (including VA purchased care) by VA chart review. We estimated the minimum sample size needed to ensure adequate power (80%) for a variety of assumptions (percentage of Current WEB-ED participants engaging in VA MH care, effect (odds ratios), and variance inflation factors (VIF)57, using nQuery 4.0. We anticipate random assignment will result in no statistical differences between RCT arms based on WEB-ED data (e.g., prior enrollment in VA, positive screens). However, covariates will be included (e.g., gender, rurality, patient-activation scores, VA site) in multivariate analyses to control for variation due to these other variables. Any significant covariates may point to sources of variability to explore in future research efforts, but we do not anticipate having sufficient power to conduct subsample analyses by gender or VA site.

XII. Future Research

XII.1

Do you wish to keep any information about subjects involved with this research project so that members of the current research team may contact them in the future for your own research projects?

Yes

XII.2

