Veteran RCT Recruitment (WEB-ED+) and Assignment: Veterans who screen positive on one or more MH (mental health) screens will be eligible for the RCT and asked online at WEB-ED completion for permission to re-contact them about continuing their participation in the RCT. Those who indicate yes to study re-contact will be sent IRB approved study information, including the RCT consent letter (2B), consent and HIPAA forms attached to this application. Those who decline will be thanked again for their participation and contact will be discontinued. We will use adaptive randomization to achieve balance in the assignment to the treatment intervention arm of WEB-ED+ relative to the control arm of Current WEB-ED. Participants will be sent a letter to inform them about which arm of the RCT they have been assigned to and the expected participation steps for each arm (RCT Intervention Assignment letter or RCT Control Arm Letter). Those who are assigned to the Current WEB-ED arm of the RCT (those who had positive screens for the current WEB-ED, but randomly assigned to no intervention) will not complete Web-Ed+ and will not be contacted until Phase 3. The phase 2D email - RCT will be used to follow up with subjects who have been selected for participation but have not yet completed the additional online screening per randomization.

A medical chart review will be conducted for all subjects who return the signed HIPAA and consent forms for the RCT. Chart reviews will focus on VA care the subject received (or not) including medication, therapy, & any mental health and substance use treatment. We will review the time from post-deployment through 6 months after the subject's initial study participation.

We will assess/confirm enrollment status and upcoming appointments of participating Veterans using a combination of national visual chart review using CAPRI/JLV, along with accessing enrollment and appointment data from the CDW.

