Phase 2 RCT Intervention (WEB-ED+) Provider Procedures: once the provider has agreed to participate, they will be sent an email that contains links to 2 short videos about shared decision-making and three brief decision aids (PTSD, depression, substance use disorder).

Using the knowledge both the provider and patient learned from the WEB-ED+ materials, they will discuss treatment options at the patient's appointment.

If subjects do not complete steps in the process, the appropriate attachment (Phase 2 RCT missing VA enrollment, Phase 2 RCT missing MHV premium enrollment, or Phase 2 RCT missing secure messaging) will be sent via email or postal mail if email is not available to support completion of these steps, with a toll free number provided. Further, up to 3 contact calls will be made until the subject is reached, to determine if the participant has discontinued study participation, if the study team can be of further assistance, or to determine the completion barrier(s), and if the Veteran is enrolled- to assist them with MHV barriers by sending the study screening results summary by encrypted email to the participant's preferred or new provider in their stead (eSDM Chart Review-Secure Message) so they are able to progress to their appointment in order to use shared decision-making with their provider about their positive MH screens. Requested Resources Email Scripts will be sent per request of subject as needed. The missing email notice attachment will be used for those in the treatment arm of RCT to encourage them to contact us and update their email address so we can continue their participation with the study. The provider consent notification document will be sent via mail or email letting the participant know that their provider has consented to participate in the RCT.

Those who decline will be thanked again for their participation and contact will be discontinued. We will use adaptive randomization to achieve balance in the assignment of those who consent to WEB-ED+ or Current WEB-ED. Those who are assigned to Current WEB-ED will not be contacted again until Phase 3.

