Per VA Research project modification approval received November 2022, we are now able to provide subjects with an additional \$30 for already returned signed HIPAA form and consent to participate with this study phase. We will notify previous subjects using attachments (Phase 2 New Reimbursement postal mail and Phase 2 New Reimbursement email), and submit this request, anticipating that they should receive this direct deposit within 4 to 8 weeks. For new RCT recruitments we have edited the Phase 2 RCT recruitment to indicate that if they return their signed HIPAA form and consent to participate in this study phase they will receive \$50.00 (the same amount as those who have already returned these forms will receive).

Because of new VA research policy changes, we are now also able to provide subjects with an additional \$75.00 upon completion of the RCT "intervention group" steps of this research phase that involves seeing their VA provider (as described in the consent and the

encrypted study group assignment email).

We will send the new funding notice to all RCT consenters first by email, followed by postal mail with follow up a week later via telephone using a 3-call protocol.

If subjects do not complete the screening, attachments Phase 2G Incomplete Survey Email and Phase 2H Incomplete Survey Letter will be sent to encourage completion.

A medical chart review will be conducted for the subjects who return the signed HIPAA and consent forms for the RCT and prior to the interview for phase 3. Chart reviews will focus on VA outpatient care the subject received (or not) including medication, therapy, & substance use treatment. We will review the time from post-deployment through 6 months after the subject's initial study participation. We will assess/confirm enrollment status and upcoming appointments of participating Veterans using a combination of national visual chart review using CAPRI/JLV, along with accessing enrollment and appointment data from the CDW.

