participant HIPAA and consent forms allowing for consequent VA chart review and with the Veteran's VA provider for all assigned to the RCT portion of Phase 2. Given a recent VA research modification that allows us to reimburse an additional \$30 to those who have already returned signed HIPAA and consent forms necessary to be reimbursed will be contacted about this increase in reimbursement as well as the new policy change that allows us to reimburse \$75.00 for completion of the "intervention group" requirements. Those in the RCT will be notified about this change and those newly recruited will have this change included in their initial recruitment and consent documents. Participants need to sign and return a bank form to initiate the electronic deposit(s). Those who have already done and are eligible for the additional reimbursement will not need to do so again. The Bad Address Contact Call script will allow the research team to confirm the correct mailing address to send forms to the participant. If the research team is unable to reach the Veteran by phone, the Bad Address Contact Email will be sent. The reimbursement follow up script and email will be used to see if the participant would like reimbursement materials resent so they can be compensated.

In summary: Per project modification approval received November 2022 (attached), we are now able to provide subjects with an additional \$30 for already returned signed HIPAA form and consent to participate with this study phase. We will notify previous subjects using attachment (Phase 2 New Reimbursement postal mail and Phase 2 New Reimbursement email), and submit this request, anticipating that they should receive this direct deposit within 4 to 8 weeks.

Because of new policy changes, we are now also able to provide subjects with an additional \$75.00 upon completion of the RCT "intervention group" steps of this research phase that involves seeing their VA provider by March 1, 2023 (as described in the consent and the encrypted study group assignment email). Those who have returned consents and HIPAA forms for the RCT will be notified of this change and encouraged to complete their RCT intervention steps if they have not already. Those newly recruited to the RCT will have this included in their updated Phase 2 RCT consent document.

Phase 3: \$40 will be compensated for each participant (76) who completes the Phase 3 semi-structured Veteran interviews.

VIII. Risks

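### Controls are not to be contacted before Phase 3, yet the new payment notice goes to all RCT consenters and may prompt some controls inside the outcome window

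*Combined protocol and SAP*

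**What the plan says.** **Contact rule for controls.** VII.E.6 of the IRB application states: "Those who are assigned to Current WEB-ED will not be contacted again until Phase 3". VII.D.29 says the same of Veterans randomised to no intervention, who "will not complete Web-Ed+ and will not be contacted until Phase 3". The sample-size text (protocol section 4.0, Aim 2; application XI.2) assumes that the control arm has no additional participation activities.

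**The notice.** Shortly after the no-contact sentence, VII.E.6 says "We will send the new funding notice to all RCT consenters first by email, followed by postal mail". Up to three telephone calls are to come after the mailing. The paragraph just before it introduces $75 for completing intervention-group steps that involve seeing the VA provider.

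**Who the consenters are.** VII.E.6: "We will use adaptive randomization to achieve balance in the assignment of those who consent to WEB-ED+ or Current WEB-ED". Consenters therefore include both arms.

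**Compensation section (VII.E.19).** "Those in the RCT will be notified about this change". Veterans who returned RCT forms are to be contacted about an additional $30 for those forms and about the $75. They "will be notified of this change and encouraged to complete their RCT intervention steps if they have not already". No restriction by arm is given.

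**Outcome.** The primary outcome is VA mental health services receipt, yes or no (XI.1). It is read from charts through 6 months after initial participation (VII.E.6), or 6 months after WEB-ED completion (protocol section 4.0, chart review).

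**The concern.** The contact rule and the notice cannot both be followed for a control who has returned the RCT forms. As written, that control gets an e-mail, a letter and up to three calls about a payment change that includes money for seeing a VA provider. Seeking VA care is close to the behaviour the trial measures.

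Two things are at stake. Some controls may be prompted while their 6-month outcome is still being counted. The comparator also stops being one condition: controls followed before the notice had no such contact, and those followed across it did. The analysis plan does nothing to separate the two periods.

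**Working it through.** **1. Do the passages conflict?**

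| Question | VII.D.29 and VII.E.6, contact rule | VII.E.6 and VII.E.19, notice |
|---|---|---|
| Are controls contacted before Phase 3? | No | Yes, as RCT consenters |
| By what route? | None | E-mail, post, 3-call protocol |
| On what subject? | Not applicable | $30 for forms; $75 for steps that include a VA visit |
| Limited by arm? | Controls only | No limit stated |

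Both sides stand in the current form text, not only in the old-value/new-value log. No passage exempts controls from the notice or amends the contact rule.

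**2. Can the notice fall inside the outcome window?** Only for controls within 6 months of their start when it is sent. The new attachments are dated 12/14/22 to 12/19/22, so a send date around December 2022 is an inference. XIII.2 says enrolment had not stopped. Total reported subjects were 631 on 04/05/22 and 1,575 on 03/21/23, a rise of 1,575 − 631 = 944. Some controls were very probably in window. The number cannot be derived, because these totals are neither RCT consenters nor controls, and their timing within the interval is not given.

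**3. How sensitive is the trial? (Illustration only.)** The documents give no effect size for the notice.

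The plan's own figure comes first. For a control rate of 25% and OR 1.5, the WEB-ED+ rate is 0.25 × 1.5 / (0.75 + 0.375) = 33.3%. The pooled-variance formula at 2:1, 80% power and one-sided 5% gives 278 controls, and 278 × 3 = 834, the first cell of the sample-size table. Two-sided 5% gives 1,059. The plan states neither alpha nor sidedness; two-sided 5% is assumed below.

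Power = Φ{[d − 1.96 √(p̄q̄(1/650 + 1/450))] / √(p₁q₁/650 + p₂q₂/450)}, with the plan's 650 WEB-ED+ completers and 450 controls. At 33.3% against 25%: (0.0833 − 1.96 × 0.0281) / 0.0275 ≈ 1.03, so power is 85%.

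If the average control rate rises and WEB-ED+ stays at 33.3%:

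| Rise in control rate (points) | OR | Power |
|---|---|---|
| 0 | 1.50 | 85% |
| 1 | 1.42 | 74% |
| 2 | 1.35 | 61% |
| 3 | 1.29 | 47% |
| 5 | 1.17 | 21% |

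Starting from control rates of 30% and 35%, power goes from 88% and 90% with no rise to 28% and 34% at +5 points.

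**4. Why the table is one-sided.** The rises are averages over the whole control arm. If half the controls were in window (an assumption), a 2-point average needs 4 points in each of them. WEB-ED+ Veterans also get the notice and can earn the $75. If both arms rise by 3 points, OR = (0.363/0.637) / (0.28/0.72) = 1.47. If WEB-ED+ rises by 5 and controls by 2, OR = (0.383/0.617) / (0.27/0.73) = 1.68, above the planned 1.50. The movement can go either way.

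**The case against.** The e-mail, letter and call script are attachments that are not shown, so arm-specific wording cannot be excluded. Controls have no intervention steps and cannot earn the $75, so the encouragement is most naturally read as meant for WEB-ED+ Veterans. No-contact was also never absolute: VII.D.29 sends an assignment letter to both arms, and controls are owed the $30, which requires some contact. On this reading the no-contact sentence means no intervention contact, and the defect is one of drafting.

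Most of this stands. It rules out treating the text as proof that controls were urged to seek care. It does not remove the conflict. The protocol text is what staff follow, it names all consenters, and VII.E.19 joins the $30 and the $75 in one communication without separating the arms. If separate wording was intended, the plan should say so.

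It is also fair that Veterans recruited later see the $75 in the consent document before assignment, so separate notices cannot make all controls alike.

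**Conclusion.** The contradiction is certain, and the passages must be reconciled. Followed as written, the notice changes the control condition during the trial and may prompt some controls inside their outcome window. This rests on three assumptions: that the notice carries the $75 content to both arms, that some controls were within 6 months of their start, and that the contact affects care-seeking. The first two are plausible from the text; the third is inference.

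A reader might infer that the notice raises control engagement, dilutes the contrast and cuts power to as little as 21%. The documents do not support that. That figure holds WEB-ED+ fixed although that arm gets the same notice, and it applies an assumed 5-point rise to every control. Neither the size nor the net direction of bias can be derived, so the power figures show sensitivity and are not a forecast. The change is still worth making because it is cheap and bears directly on the primary outcome.

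**What to change.** - Reconcile VII.D.29 and VII.E.6 with the notice text in VII.E.6 and VII.E.19. Reword the no-contact sentence to allow administrative payment contact.
- State that already-assigned controls receive only the form-return payment notice. The visit-payment wording, the encouragement to complete steps and the 3-call follow-up go to WEB-ED+ only.
- Record the date each notice was sent.
- Add a sensitivity analysis that counts VA mental health services receipt in both arms only up to the notice date, censoring follow-up there. Use the send date, not the date a Veteran was reached by telephone, so that the cut-off does not depend on response. This is better than keeping only Veterans whose 6-month window had closed. With a December 2022 notice, those Veterans would have started by about June 2022, and only 631 subjects in total had been reported by April 2022.

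If the notice has already gone out, separate letters no longer help, but the text correction, the recorded dates and the sensitivity analysis still apply.

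**Cost.** A second letter version and one extra analysis. Separation is only partial, because new recruits see the $75 in the consent form. The sensitivity analysis will have fewer events and can only support the primary result.
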